Statistical support will be provided by [name]., Professor in the Department of Clinical Sciences, Division of Biostatistics at UT Southwestern Medical Center at Dallas. Descriptive statistics (i.e., group characteristics such as age, body mass, BSA burned, physical activity questionnaire data, etc.) will be analyzed via one-way analysis of variance to compare the three study groups. Within each environmental exposure, the primary evaluation will address an expected interactive effect of group and the employed cooling condition (e.g., Conditions A-D as outlined in Table 1) on the magnitude of the elevation in internal body temperature to 60 min of exercise. These data will be statistically analyzed via a two-factor mixed-effects model repeated measures analysis with main factors of group and the applied cooling condition (crossover repeated factor), and their interaction, with subject modeled as a random effect and specifying covariance structure, using SAS Proc Mixed. Potential mechanisms contributing to differing elevations in internal body temperature (e.g., differences in magnitude of changes in skin temperature and skin surface water vapor pressure) as a result of the exercise bouts will be statistically evaluated via the same approach. The extent and significance of the expected interactions will be statistically explored post-hoc with appropriate comparisons derived from the models' least square means contrasts, applying Bonferroni type adjustments for multiple testing.

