We estimated power to detect a 0.5 °C mean difference in the elevation in internal body temperature to the exercise bout between groups. This number was obtained from one of our prior studies in which similar thermoregulatory responses to exercise in burn survivors were assessed, with a standard deviation of the elevation in internal body temperature being ~0.3 °C. Based upon these estimates, 12 subjects per group for each environmental exposure would provide omnibus power of 0.94 for group differences in the elevation in internal body temperature of 0.45 °C at an alpha of 0.05 and power of 0.84, using an adjusted alpha of 0.0125 to account for multiple comparison evaluations of the four interventions between groups. For the within group comparison, power is >0.9 to detect a difference in the increase in internal body temperature of 0.4 °C at an alpha of 0.0125 (power analyses from: NCSS PASS 15). Nevertheless, we will enroll 18 subjects per group (9 male and 9 female) for each environmental exposure to allow for attrition as well as provide additional power to evaluate any sex-related differences, should they become apparent. Randomization within groups for the order of the applied cooling modality will be implemented with a Latin square blocking design.

Form A

IRB # 30204 | STU-2020-0334

4.b. List of the study intervention(s) being tested or evaluated under this protocol

	N/A - this study does not test or evaluate an intervention. Skip to item 4.d.		
#	Study intervention(s) being tested or evaluated under the protocol Add or delete rows as needed	Affiliate Place a check next to institution(s) where the intervention will be performed	Local Standard Practice? Indicate whether the intervention is considered acceptable practice locally for applicable institutions
1	Skin cooling (fan and skin wetting)	 UTSW	 Yes
		 PHHS	 Yes
		 CMC	 Yes
		 THR	 Yes
		 TSRH	 Yes
		 Other: _____	 Yes

4.c. Risk:Benefit Analysis of study interventions being tested or evaluated under this protocol

For each study intervention identified in section 6b above, complete a risk:benefit analysis table.

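### Does the sample size need a new justification because no power is given for the primary group-by-cooling interaction?

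*Combined protocol and SAP*

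**What the plan says.** Both statements stand in section 4.a (research methods) of the combined protocol and SAP.

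- **Primary test.** Within each environmental exposure, "the primary evaluation will address an expected interactive effect of group and the employed cooling condition" on the rise in internal temperature at 60 minutes of exercise. The model is a "two-factor mixed-effects model repeated measures analysis with main factors of group and the applied cooling condition (crossover repeated factor), and their interaction", with subject as a random effect. Contrasts of least-squares means, with a Bonferroni-type adjustment, follow post hoc.
- **Power between groups.** The paragraph opens with "We estimated power to detect a 0.5 °C mean difference in the elevation in internal body temperature to the exercise bout between groups" and a "standard deviation of the elevation in internal body temperature being ~0.3 °C". It then states that 12 per group "would provide omnibus power of 0.94 for group differences in the elevation in internal body temperature of 0.45" °C at alpha 0.05, and 0.84 at alpha 0.0125.
- **Power within group.** "For the within group comparison, power is >0.9 to detect a difference in the increase in internal body temperature" of 0.4 °C at alpha 0.0125.
- **Enrolment.** "we will enroll 18 subjects per group (9 male and 9 female) for each environmental exposure to allow for attrition", and also to look at sex-related differences.

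No interaction size, set of cell means, within-subject correlation or interaction power is given.

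**The concern.** A sample size is normally justified by the power of the primary test. Here the primary test is an interaction, and the power quoted is for two other quantities. The interaction measures how much the gap between groups changes from one cooling condition to another. If burned subjects ran 0.45 °C hotter than controls in every condition, and cooling lowered every group by 0.4 °C, both stated targets would be met in full. The primary test would still reject only 5% of the time at any sample size.

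What is at stake is the reading of a non-significant interaction. Someone who takes 0.94 and >0.9 as the power of the primary test could conclude that cooling works equally in burned and non-burned people, when the trial may have had little chance of seeing a partial difference.

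**Working it through.** **1. Reproduce the plan's figures.** Inputs from section 4.a: n = 12 per group, difference 0.45 °C, SD 0.3 °C, alpha 0.05 and 0.0125. Two-sided tests are assumed.

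Pairwise group contrast with error pooled over three groups, df = 3 × 11 = 33. Noncentrality = (0.45/0.3) × √(12/2) = 1.5 × 2.449 = 3.674.

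| Reading | Alpha 0.05 | Alpha 0.0125 |
|---|---|---|
| Plan | 0.94 | 0.84 |
| Contrast, 33 df | 0.946 | 0.842 |
| Two-sample t, 22 df | 0.939 | 0.819 |
| Three-group F, evenly spaced, range 0.45 °C | 0.891 | 0.736 |
| Three-group F, evenly spaced, range 0.5 °C | 0.947 | 0.842 |

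The pair is attainable, and no interaction term is needed to obtain it. Which test was meant by omnibus is unclear, but that does not affect this point.

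Within group: paired t, n = 12, 11 df, 0.4 °C, alpha 0.0125. SD of differences = 0.3 × √(2(1 − ρ)), where ρ is the within-subject correlation.
- ρ = 0.5: SD 0.300, noncentrality (0.4/0.300) × √12 = 4.62, power 0.925.
- ρ = 0.3: SD 0.355, noncentrality 3.90, power 0.80.

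On this reading, power above 0.9 needs ρ of about 0.46. With a pooled 99-df error term it needs about 0.28.

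**2. Power of the interaction test.** F test with 6 and 9(n − 1) df: 99 at n = 12, 153 at n = 18. Noncentrality λ = n × Σγ² / (SD² × (1 − ρ)), where γ are the interaction effects in the 3 × 4 table.

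Assumptions, none of them in the documents: compound symmetry; evenly spaced groups; a 0.45 °C gap between the extreme groups under control; ρ of 0.3, 0.5 or 0.7. SD is the plan's 0.3 °C and alpha is 0.05.

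With evenly spaced groups, Σγ² = 0.5 × (sum of squared deviations of the four condition gaps from their mean).

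Worked case, every modality halves the gap: gaps 0.45, 0.225, 0.225, 0.225. Squared deviations sum to 0.225² × 3/4 = 0.03797, so Σγ² = 0.01898. At n = 18 and ρ = 0.5, λ = 18 × 0.01898 / (0.09 × 0.5) = 7.59, and power is 0.49.

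| Assumed pattern | Σγ² | Power at n = 18, ρ = 0.3 / 0.5 / 0.7 |
|---|---|---|
| Gap equal in all conditions | 0 | 0.05 / 0.05 / 0.05 |
| All three modalities halve it | 0.0190 | 0.35 / 0.49 / 0.74 |
| Only the two wetting conditions halve it | 0.0253 | 0.46 / 0.63 / 0.87 |
| Wetting halves it, fan alone widens it by 0.10 °C | 0.0403 | 0.70 / 0.86 / 0.98 |
| All three close three quarters | 0.0427 | 0.73 / 0.88 / 0.99 |
| All three abolish it | 0.0759 | 0.95 / 0.99 / 1.00 |

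At n = 12, halving by all three gives 0.23 / 0.32 / 0.53, and abolition gives 0.80 / 0.93 / 1.00. Simulation agrees: 0.346 / 0.484 / 0.744 for halving at n = 18, and 0.051 for the equal-gap case.

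**3. What the alternatives would buy.** Replacing the 6-df test by a single contrast of gap changes (0.225 °C, n = 18, 153 df) gives 0.47 / 0.61 / 0.82, against 0.35 / 0.49 / 0.74. Keeping the 6-df test and seeking 80% power when all modalities halve the gap takes about 46 / 34 / 21 completers per group.

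**The case for a change.** The strongest case for a change is that the plan commits itself to one primary test and leaves the reader unable to judge whether 12 or 18 per group suffices for it. The six extra subjects are assigned to attrition and sex differences, not to the interaction. If cooling narrows but never reverses the gap, the change in gap cannot exceed 0.45 °C, so the group difference would be the most the interaction could be. With partial closing, power can fall well below 0.8. The repair looks cheap: one calculation and a paragraph.

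Part of this stands. The quoted power must not be carried over to the interaction, and a power statement for it would have been good reporting.

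The rest is weaker. The upper bound holds only if every modality narrows the gap. The background section describes severely blunted sweating in injured skin, so a fan alone could help non-burned subjects more and widen the gap while wetting narrows it. Nor is a missed interaction generally likely under partial closing: three-quarters closing gives 0.73 / 0.88 / 0.99 at 18 per group. The lowest correlation used, 0.3, sits badly with the plan's own within-group figure if that came from a paired t test. The move from 0.5 to 0.45 °C is unexplained, but planning for a smaller difference than the one first named is conservative.

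**Conclusion.** The gap in the write-up is real, but no change to the plan follows.

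- The sample-size paragraph names its quantities correctly, and 12 per group delivers them. It claims no interaction power that the design then fails to reach.
- Whether the interaction is adequately powered is undetermined. With 18 completers per group the answer runs from 0.35 to 1.00 across the non-null patterns and correlations above, and the documents supply neither input that would settle it. Inadequacy has not been shown.
- A power paragraph would change neither the data collected, nor the model, nor the test. A non-significant interaction should be read through the adjusted contrasts and their confidence intervals, which the planned model can supply, and not through 0.94 or >0.9.
- The changes that would alter the analysis are trade-offs. A single contrast gains moderately if the chosen pair is right and discards the other conditions. Making the within-group comparison primary turns the between-group question into a secondary one. Changing the primary hypothesis in a document dated May 2024 under a 2020 IRB number may carry its own cost, as enrolment status is not stated. More subjects would mean up to about 46 completers per group under the least favourable halving case in the table.
- The between-group and within-group comparisons that are powered serve the stated purpose of identifying cooling modalities that work.

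The interaction figures rest on SD 0.3 °C, compound symmetry, evenly spaced groups and the assumed gap patterns. Each applies to its own pattern only.

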these individuals enjoy the rehabilitative and health benefits of physical activity and curtail adverse consequences of a sedentary lifestyle.

b. Current practice

N/A

3. Study Design.

Describe the study design (e.g., single/double blind, parallel, crossover, etc.) Consider inserting a scheme to visually present the study design.

We will conduct a randomized crossover design study. Non-burned control subjects, subjects who experienced burns covering ~20% to 40% of their body surface area, and subjects having burns >40% of their body surface area will be investigated. In one of the three environmental conditions outlined in Table 1, subjects will exercise while receiving one of the indicated cooling modalities.

Table 1: Proposed environmental conditions and cooling modalities.

Environmental Conditions	Condition A	Condition B	Condition C	Condition D
24 °C; 40% RH	Control (no fan or skin wetting)	Skin wetting only	Fan only	Skin wetting with a fan
30 °C; 40% RH	Control (no fan or skin wetting)	Skin wetting only	Fan only	Skin wetting with a fan
No higher than 40 °C; 40% RH	Control (no fan or skin wetting)	Skin wetting only	Fan only	Skin wetting with a fan

Table 2: Procedures and visits

	Visit 1	Visit 2	Visit 3	Visit 4	Visit 5
Informed Consent	X				
Urine Sample	X	X	X	X	X
Body Composition (DXA)	X				
Exercise Test	X				
12 lead ECG	X				
Alcohol Intake Survey	X				
International Physical Activity Survey	X				
Screening Questionnaire	X				
Heart Rate	X	X	X	X	X
Blood Pressure	X	X	X	X	X
Internal Temperature		X	X	X	X
Skin Temperature (including infrared imaging)		X	X	X	X
Skin blood flow and sweating measures		X	X	X	X
Blood samples		X	X	X	X

Form A

IRB # 30204 | STU-2020-0334

Metabolic Rate & ventilation		X	X	X	X
Perceptual Survey		X	X	X	X
Echocardiogram	X	X	X	X	X

4. Research Plan / Description of the Research Methods:

4.a. Provide a comprehensive narrative describing the research methods.

- 1) Provide the order in which tests/procedures will be performed,
- 2) Provide the setting for these events and a description of the methods used to protect privacy during the study.
- 3) Provide the plan for data analysis (include as applicable the sample size calculation)

Please respond to all components of this item, or clearly indicate which components are not applicable.

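### Is the adjusted alpha of 0.0125 wrong because it divides by the four conditions and ignores the three group pairs within each?

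*Combined protocol and SAP*

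**What the plan says.** Section 3 (Study Design) defines three groups: "Non-burned control subjects, subjects who experienced burns covering ~20% to 40% of their body surface area, and subjects having burns >40" per cent. Each subject completes all four cooling conditions at a given environmental temperature.

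In the data analysis paragraph of section 4.a, "the primary evaluation will address an expected interactive effect of group and the employed cooling condition". Follow-up comes second: "The extent and significance of the expected interactions will be statistically explored post-hoc with appropriate comparisons derived from" the model's least-squares means, "applying Bonferroni type adjustments for multiple testing". The contrasts are neither listed nor counted.

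The sample size paragraph opens with "We estimated power to detect a 0.5 °C mean difference in the elevation in internal body temperature" and an SD of about 0.3 °C. For 12 subjects per group it then reports "omnibus power of 0.94 for group differences in the elevation in internal body temperature of 0.45 °C at an alpha of 0.05", followed by "power of 0.84, using an adjusted alpha of 0.0125 to account for multiple comparison evaluations of the four interventions between groups". It closes by stating that "we will enroll 18 subjects per group (9 male and 9 female) for each environmental exposure to allow for attrition" and to add power for sex-related differences.

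**The concern.** Three groups give three pairs per condition, and four conditions give 3 × 4 = 12 between-group pairs in each environment. An alpha of 0.0125 = 0.05/4 allows for the conditions only. If the 0.84 is meant for a pair of groups, two things could go wrong, and they are alternatives:

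- The final analysis applies Bonferroni to all 12 pairs (alpha 0.05/12 = 0.0042). Error is then controlled, but the stated power is too high for 12 per group.
- The final analysis tests every pair at 0.0125, and the family-wise error could exceed 0.05.

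The text also gives two planning differences, 0.5 °C and 0.45 °C, so a reader cannot be sure which test produced 0.94 and 0.84.

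**Working it through.** **Inputs** (section 4.a, sample size paragraph): SD 0.3 °C; difference 0.45 °C, with 0.5 °C also named; n = 12 per group for the power figures and 18 to be enrolled; alpha 0.05 and 0.0125. Three groups and four conditions come from section 3. Two-sided tests are assumed, since sidedness is not stated.

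**Step 1: the divisor.** 0.05/4 = 0.0125, exactly.

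**Step 2: the stated power as a pair of groups.** Noncentrality = difference / (SD × √(2/n)) = 0.45 / (0.3 × √(2/12)) = 3.674. With error pooled over three groups (33 df), the critical t is 2.034 at 0.05 and 2.642 at 0.0125, so power is 0.946 and 0.842. With a two-sample t test (22 df) it is 0.939 and 0.819.

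**Step 3: the stated power as a three-group F test within one condition.** Noncentrality = n × Σ(group mean − grand mean)² / SD², with 2 and 33 df. The critical F is 3.285 at 0.05 and 5.019 at 0.0125.

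| Group means (°C) | Noncentrality | Power at 0.05 | Power at 0.0125 |
|---|---|---|---|
| 0 / 0.225 / 0.45 | 13.50 | 0.891 | 0.736 |
| 0 / 0.04 / 0.45 | 16.54 | 0.945 | 0.839 |
| 0 / 0 / 0.45 | 18.00 | 0.961 | 0.875 |
| 0 / 0.25 / 0.5 | 16.67 | 0.947 | 0.842 |

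Three set-ups therefore come close to the published 0.94 and 0.84: a pooled-error pair at 0.45 °C, an F test at 0.45 °C with the middle mean near one end, and an F test with means evenly spaced over 0.5 °C. The documents do not settle which was used. None shows the 0.84 to be miscalculated, and for either F test 0.05/4 is the right divisor for four tests.

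**Step 4: the least favourable reading.** Take 0.84 as the power for a pair, and apply single-step Bonferroni to all 12 pairs (alpha 0.05/12 = 0.0042).

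| n per group | Two-sample df | Pooled df |
|---|---|---|
| 12 | 0.679 | 0.719 |
| 15 | 0.826 | 0.851 |
| 16 | 0.861 | 0.881 |
| 18 | 0.913 | 0.927 |

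To keep 0.84, the number completing per group rises from 12 to 15 (pooled) or from 13 to 16 (two-sample). Of 18 enrolled, the tolerable losses fall from 6 to 3, or from 5 to 2. If only the eight burn-versus-control pairs were adjusted (alpha 0.00625), power would be 0.734 to 0.767 at 12 and 0.935 to 0.945 at 18.

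**Step 5: the error rate.** Suppose all 12 pairs were tested at 0.0125 after nothing more than a significant interaction. In simulations with assumed within-subject correlations of 0.3 to 0.7 (none is given in the documents), family-wise error is about 0.06 to 0.10 when one group differs by 0.45 °C in one to three conditions and all groups are equal in the rest. If the groups are not all equal in any condition, at most one pair per condition is truly null, and the bound is 4 × 0.0125 = 0.05. Requiring each condition's F test to be significant at 0.0125 first kept the error at or below 0.05 in every case simulated.

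**The case for a change.** The strongest case for a change is that the protocol itself powers these comparisons and promises to adjust them, so the family ought to be fixed before the data are seen; otherwise the divisor could be chosen afterwards. No attrition rate is given, and a fall in tolerable losses from 6 to 3 of 18 is not trivial. An effective cooling modality, which is the aim of the study, could make the groups equal in some conditions, and that is the pattern in which testing pairs at 0.0125 inflates the error.

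Part of this stands. The contrasts are unlisted, the test behind 0.84 is unnamed, and two planning differences appear. The same looseness affects the within-group comparisons, also planned at 0.0125, where four conditions give six pairs. A line naming the test and the contrasts would help a reader.

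The rest does not carry. The inflated error belongs to a rule that the plan does not state: 0.0125 appears only in the power paragraph, and testing 12 pairs at 0.05/4 would not be the Bonferroni-type adjustment that the analysis paragraph commits to. The figure of 0.68 to 0.72 assumes the strictest single-step form over the largest between-group family, with only 12 completing. Holm's method is also of Bonferroni type; with the same 12 pairs and 12 per group it gave 0.72 to 0.79 in simulation, with family-wise error at most 0.041.

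**Conclusion.** No stated number is shown to be wrong. The 0.0125 is correct for four three-group tests, one per condition, and 0.84 at 12 per group is attainable under that reading or as a single pair. The missing contrast list is a gap that analysts can fill within the Bonferroni-type commitment already made. Choosing between all 12 pairs, the eight burn-versus-control pairs, and pairs gated by each condition's F test is a trade-off: which has more power depends on the contrasts of interest and on where the middle group lies.

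Even on the strictest reading, power for a 0.45 °C pair is 0.91 to 0.93 if all 18 per group complete, and 0.83 to 0.85 with 15. Only near 12 per group does it fall to about 0.7. The primary interaction test and the planned enrolment are unaffected. This rests on the plan's SD of 0.3 °C, two-sided tests and equal group sizes.

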The setting for all visits will be the Institute for Exercise and Environmental Medicine. Subjects will be recruited from: 1) the UTSW or IEEM volunteer research registry, 2) flyers/advertisements posted/shared at major burn centers throughout the United States, 3) info-articles and email blasts disseminated by our collaborator, the Phoenix Society, which is the largest burn support group in North America, as well as smaller (i.e., regional) burn support groups, 4) database of burned soldiers via our collaboration with the US Army, and 5) database of burn survivors maintained at UT Southwestern by the Co-Investigator ([name]) IRB protocol number: Study00000105. The latter database will be accessed by the Study Team to identify burn survivors who meet the inclusion/exclusion criteria outlined in Form C. Those individuals will be informed of the study, along with instructions to contact the Study Team should they be interested in participating.

Trials will be conducted in controlled laboratory settings. Burn survivors and non-burned individuals will perform bouts of exercise at a given environmental temperature as outlined in Table 1. Subjects will be required to perform exercise across all four of the conditions (i.e., Conditions A-D in Table 1) for a given environmental temperature. However, a subject will not be required to perform the battery of trials across all three environmental temperatures. Within a particular environmental temperature, the order of exposure for Conditions A-D will be randomized. Prior to being assigned to an order of cooling modalities for any given environmental temperature, we will obtain participant demographics, anthropometrics (body mass, height and composition) and aerobic capacity data.

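### Order of cooling conditions is blocked in fours within group only, but 18 per group and 9 per sex are not multiples of four, and the listed model has no visit term

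*Combined protocol and SAP*

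**What the plan says.** All of this is in section 4.a of the combined protocol and SAP.

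- Each subject completes every cooling condition at a given environmental temperature: "Subjects will be required to perform exercise across all four of the conditions". The order is random: "Within a particular environmental temperature, the order of exposure for Conditions A-D will be randomized".
- The method is given in one sentence: "Randomization within groups for the order of the applied cooling modality will be implemented with a Latin square blocking design". The stated stratum is the group. Sex is not mentioned there.
- The powered size is 12 per group: "12 subjects per group for each environmental exposure would provide omnibus power of 0.94". Enrolment is set higher: "we will enroll 18 subjects per group (9 male and 9 female) for each environmental exposure to allow for attrition". The same sentence gives power for sex-related differences as a second reason.
- The primary analysis is a mixed model with group, cooling condition, their interaction and a random subject effect. No visit (period) or sequence term is listed.

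The section does not say how an incomplete last block is filled, or what happens to the sequence of a subject who drops out.

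**The concern.** In a crossover, each condition should fall equally often on each visit, so that a trend over visits (acclimation, familiarity with the task, season) does not leak into the condition contrasts. Latin-square blocking does this when the number of subjects is a multiple of four. The powered 12 is such a multiple; the enrolled 18 and the 9 per sex are not.

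There are two consequences. Within a group, the two leftover sequences leave a small imbalance. It can differ between groups and so enter the group-by-condition interaction, which is the primary evaluation. Within a sex, nothing in the stated scheme balances order, because men and women share the same blocks. A model with a visit term would absorb a common trend in either case, but the listed model has none.

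**Working it through.** **Inputs from section 4.a.** Four conditions; 12 per group for power; 18 enrolled per group (9 + 9); SD of the temperature elevation about 0.3 °C; target differences 0.5 and 0.45 °C between groups and 0.4 °C within group.

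**Assumptions.** A linear drift of 0.05–0.15 °C per visit; the documents give no drift. Drop-out is of whole subjects, at random. The drop-out rate is not stated; 12 out of 18 implies an allowance of 6/18 = 1/3.

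**1. The plan's own power figures.** With 12 per group and SD 0.3, a two-group t test at 0.45 °C gives 0.94 at alpha 0.05 and 0.82 at 0.0125. A three-group F test with equally spaced means spanning 0.5 °C gives 0.95 and 0.84. The stated 0.94 and 0.84 are thus reproduced to within two points, and this point does not affect them.

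**2. Whole squares.** 12/4 = 3. 18/4 = 4.5, that is four squares and two subjects. 9/4 = 2.25, that is two squares and one subject. Exact balance at 18 would need 4.5 subjects per condition per visit, which no list can supply.

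**3. All 18 finish.** Four full squares put each condition on each visit 4 times. Two rows of a fifth square raise some of these counts to 5. Over two rows a condition's positions sum to between 1 + 2 = 3 and 3 + 4 = 7, so mean positions differ by at most (7 − 3)/18 = 0.22 visits. Drawing the leftover rows at random from the 576 possible 4×4 squares, the largest gap averages 0.15 visits and is zero in about 17% of draws.

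- Effect on a within-group condition contrast: at most 0.22 × 0.05 = 0.011 °C to 0.22 × 0.15 = 0.033 °C.
- Effect on the difference of such a contrast between two groups: at most 0.44 visits, or 0.022–0.066 °C.

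**4. One sex.** Taking 9 of the 18 sequences at random as one sex, the largest gap averages 0.66 visits, or 0.03–0.10 °C under the same drift.

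**5. Drop-out.** If a random 12 of 18 finish, the largest gap averages 0.48 visits, or 0.02–0.07 °C. For a single pre-chosen pair of conditions, the SD of the gap is 0.34 visits (0.02–0.05 °C).

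**6. Re-blocked list.** Use two full squares per sex, plus a mirror-image pair for the ninth man and ninth woman, for example A-B-D-C and C-D-B-A. Position sums over the pair are A 1 + 4, B 2 + 3, C 4 + 1 and D 3 + 2, all equal to 5. Average largest gap in visits:

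| Scenario | As stated | Re-blocked |
|---|---|---|
| All 18 in a group | 0.15 | 0 |
| 9 of one sex | 0.66 | 3/9 = 0.33 |
| Random 12 of 18 finish | 0.48 | 0.45 |

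The new list cures the full group and halves the within-sex gap. It does almost nothing for drop-out.

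**7. Cost of a visit term.** Relative efficiency of condition contrasts, with visit effects estimated within one group using a four-sequence square: 0.994 at 18 (sequence counts 5/5/4/4), 0.988 at 9 (3/2/2/2) and 0.944 for 12 finishers split 4/4/2/2. A more lopsided 5/4/2/1 gives 0.875.

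**The case against.** The strongest reply is that this is ordinary block remainder. At 18 the cell counts differ by one subject, and the largest gap averages 0.15 visits, against 0.63 for unrestricted random orders, so the blocking still does most of its work. The plan never promises exact balance at 18. The drift is assumed and could be zero. Because orders are randomized, imbalance from random loss averages zero over possible lists: it is chance noise, not a bias in a known direction. Some losses even restore balance, since 16 or 12 finishers can form whole squares. Sex is not a stated stratum, and sex differences are to be examined only if they emerge. All of this stands, and it makes the point minor.

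A reader might go further and infer that an unlucky 12 finishers would carry an error as large as the standard error of a within-group contrast: 0.83 × 0.15 = 0.12 °C against 0.3/√12 = 0.087 °C. The documents do not support that. It combines the top of an assumed drift range, the full one-third loss, the 95th percentile of the gap and the worst of six pairs, and sets this against the standard error of a single contrast. That standard error takes 0.3 °C as the SD of a within-subject difference. The plan gives 0.3 °C as the SD of the elevation itself; the two agree only if the within-subject correlation is 0.5.

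A reader might also infer that enrolment should be cut to 16 per group to fill whole squares. That would lower the attrition allowance from 33% to 25% and give up subjects wanted for the sex comparison, and it would not protect against drop-out either.

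What the reply does not answer is that sex differences are a stated reason for enrolling 18, that order is left unbalanced within sex, and that the listed model has nothing to absorb a visit trend.

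**Conclusion.** The point holds as a low-cost improvement, not as a threat to the primary result. Exact order balance is impossible at 18 per group and 9 per sex. With all 18 finishing, the consequence for a within-group contrast is at most 0.01–0.03 °C, small against targets of 0.4–0.5 °C. The imbalance is larger within a sex (average largest gap about 0.66 visits) and grows by chance with drop-out (about 0.48 visits if a random 12 finish). Gaps in visits follow from the block structure, with random loss assumed for the 12-finisher figure. Every figure in °C also rests on the assumed drift of 0.05–0.15 °C per visit. The sample size of 12 and its power are not in question.

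**What to change.** Keep 18 per group and make two changes to section 4.a.

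1. **Randomization.** Within each environmental temperature, block order by group and sex, with two complete squares per sex. Give the ninth man and ninth woman of each group mirror-image sequences. Mean visit positions are then equal over the 18, and the average within-sex gap falls from 0.66 to 0.33 visits.
2. **Model.** Add visit (period) as a fixed effect to the primary mixed model and to the mechanism analyses that use the same approach. This is what handles drop-out, and it also covers the remaining within-sex gap.

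The first change costs a new randomization list and a sentence. The second costs about 1% of efficiency with all 18 and about 6% for 12 finishers split 4/4/2/2, more if the split is extreme. Neither needs extra subjects or visits.
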